# Non-English Speaking Subjects

In regards to non-English speaking subjects, a translator and/or the interpreter services provided by OHSU will be utilized for the initial consent process and any subsequent study visits to ensure the consent capacity of the subject and/or LAR and that the informed consent is being properly obtained. Short-form consent forms will be used.

# Adults Unable to Consent/Decisionally Impaired

The electrical stimulation process itself does not pose any more of a risk and/or harm on a decisional impaired patient vs. a competent patient. Subjects will have varying degrees of decisional impairment related to the indication for admission for the majority of our patients, including: fluctuating decisional impairment, progressive decisional impairment, limited decisional impairment, or complete decisional impairment. In order to assess for decision-making capacity and prior to the consent process, the study team member will assess the subject's ability to understand information about the treatment, to appreciate how that information applies to their situation, to reason with the information provided, and to make a choice and express it. If there is any doubt, the LAR will be consented.

#### 6. Procedures Involved

[figure not shown]

Figure 1. Application of E-Stim Device

Electrical stimulation will be applied to the quadriceps muscle groups on both lower extremities simultaneously for 30 minutes at a time (Figure 1). The patient will be positioned either supine or sitting.

A Vectra Neo Clinical Therapy System (Chattanooga Group) will be used to provide the stimulation. The stimulator will be set up and taken off the patients by a member of the study team or a trained ICU staff member. The stimulation parameters will be as follows:

Electrode location: Proximal and distal quadriceps

Waveform: pulsed biphasic Pulse duration: 300-450 µseconds Pulse frequency: 35 pulses per second

Amplitude: palpable, visible quadriceps muscle contraction

On/off time: 10 seconds on, 30 seconds off Ramp up and down time: 2 seconds each

Total treatment time:  $45 \pm 15$  minutes/day, for a total of at least 5 treatments each week (Mon-Sun), until ICU discharge or at the

discretion of the research team.

At Neuro ICU discharge, a member of the study team will assess functional recovery using the modified Rankin Scale (mRS) and the Extended Glasgow Outcome Scale (GOSE). (uploaded in eIRB) Subjects who withdraw from e-stim treatment may still be assessed with these instruments at discharge, unless they request to withdraw from data collection as well. Subjects may be withdrawn from e-stim treatment without their consent if their physician or the study team decides that it is in their best interest (e.g. due to skin irritation or burns).

All procedures will be performed as part of the research study, and not as standard of care.

#### **Historical Controls**

The Neuro ICU administration maintains databases for the purpose of safety and quality improvement. We propose to query this existing database to identify patients cared for in the Neuro ICU during the year 2016 that possess similar demographics and illness characteristics as our inclusion criteria. The ICU quality group will abstract data for us. The research team will not have access to identifiable data for the historical controls—only means from the historical controls on data such as length of stay and hospital costs. The information will be extracted using automated means from this database and Epic to capture average length of stay and length of ventilator support for the purposes of comparison as "historical controls". We will not be performing individual chart review.

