## 4. Study Design

The study will be a prospective, feasibility pilot study to estimate the effect size to power a future, full scale randomized controlled trial of electrical stimulation. The information learned in the pilot will help the team optimize study logistics for a future full-scale trial. The historical controls used for comparison will be from pooled, de-identified data pulled from quality improvement databases maintained by the Neurosciences ICU group. The research team will not have access to identifiable data for the historical controls—only means from the historical controls on data such as length of stay and hospital costs.

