## 5. Study Population

## a. Number of Subjects

There will be 22 subjects enrolled from the Neuro ICU. We will end enrollment at the end of the 2019 calendar year, whether or not the enrollment target has been met. We will compare the hospital course of the prospectively enrolled e-stim patients with pooled, de-identified historical patients identified from quality improvement databases maintained by the Neurosciences ICU group.

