# 8. Data Analysis Analysis plan

Covariates The following factors may impact outcome, and thus will be collected to assure the groups are comparable:

i. Demographics (sex, age, race)

Version Date 7/22/19

- ii. Illness information: primary admission diagnosis, severity of critical illness (Sequential Organ Failure Score (SOFA), APACHE II score)
- iii. Critical Illness Associated Complications Complications such as deep vein thrombosis, Hospital Acquired Infection, etc. will be recorded as these conditions may impact outcome.
- iv. Medications associated with Neuromuscular weakness: including but not limited to steroids, neuromuscular blockers

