#### **Group Comparisons**

The study team statistician will analyze the data, and will be blinded to treatment assignment ("Group A" and "Group B", instead of "E-Stim Group" "Historical Controls"). Descriptive statistics will be used to quantify feasibility. Mean length of stay and mean duration of intubation will be compared between the e-stim group and the historical controls using a t-test. If necessary, a linear regression model for length of stay and/or intubation duration will be used to compare between groups while controlling for the potential confounding of covariates. A Wilcoxon rank-sum test will be used to compare the exploratory functional outcome measures between groups, as the mRS and GOSE are both ordinal scales.

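### All historical controls come from 2016 while e-stim enrolment may run to the end of 2019, so any change in ICU practice between the periods would be counted as e-stim effect

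*Combined protocol and SAP*

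**What the plan says.** Section 6 (Historical Controls) defines the comparator by one calendar year: the quality database will be queried to "identify patients cared for in the Neuro ICU during the year 2016" with characteristics similar to the inclusion criteria. It adds that "The information will be extracted using automated means from this database and Epic", without chart review, and that the research team will receive "only means from the historical controls on data such as length of stay and hospital costs".

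On the treated side, section 5a says "We will end enrollment at the end of the 2019 calendar year". No start of enrolment is given. The only dated anchor is the page mark "Version Date 7/22/19".

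The efficacy analysis in section 8 (Group Comparisons) is: "Mean length of stay and mean duration of intubation will be compared between the e-stim group and the historical controls using a t-test". It then allows adjustment: "If necessary, a linear regression model for length of stay and/or intubation duration will be used to compare between groups". The covariates listed in section 8 are demographics, illness information, complications and medications. Calendar time is not among them.

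Section 4 gives the use of the result: "to estimate the effect size to power a future, full scale randomized controlled trial of electrical stimulation". No section gives a reason for choosing 2016, names another control year or plans a check for a time trend.

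**The concern.** Every control belongs to one calendar year and every treated patient to a later period, so treatment and period are the same variable. ICU stay and ventilator days can move for reasons unrelated to e-stim, such as weaning, sedation, mobilisation or bed-flow practice. The protocol's own text makes this plausible: section 3 says that early mobilisation shortens stay in Neuro ICU patients, and section 2 ends the ICU-stay outcome at an order for a lower level of care, which step-down practice can influence.

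The optional regression does not help. Adding calendar time to the covariates would not help either, because one control year contains no information on how untreated outcomes change from year to year. More controls from 2016 would narrow the interval but leave the bias as it is.

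At stake is Aim 2 and the effect size carried into the randomised trial. A favourable drift would inflate that effect size and leave the trial too small. An unfavourable drift would hide a benefit.

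**Working it through.** **The plan's own figure.** Section 8 (Power Calculation) gives 10 versus 7 days (a 3-day difference), 80% power, significance level 0.05 and 113 per group. No SD is stated, so 113 cannot be reproduced from the stated inputs alone. Taking the test as two-sided with a common SD, the normal approximation n = 2 × (1.960 + 0.842)² × SD² / 3² with SD = 8 gives 111.6, rounded up to 112; the t-based calculation gives 113. Solving backwards from 113 gives an SD of about 8.0 days. I use 8 as an assumption. The pilot size agrees with its rule: 0.20 × 226 = 45.2, about 45 = 22 + 23.

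**The gap.** If all patients enrolled during 2019, mid-2019 minus mid-2016 is three years. A patient enrolled at the version date (July 2019) comes about 2.6 to 3.6 years after a 2016 control, and one enrolled at the end of 2019 comes 3 to 4 years after. Any patients enrolled before 2019 shorten the average.

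**Assumed drift.** The documents give none, so I take a yearly fall r of 2%, 5% or 10% on the protocol's 10-day mean and no true e-stim effect:

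- Spurious reduction after y years = 10 × (1 − (1 − r)^y).
- SE of the pilot difference = 8 × √(1/22 + 1/23) = 2.39 days.
- False-positive rate: two-sided noncentral t, 43 df, noncentrality = reduction / 2.39.

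| Gap | Yearly fall | Spurious reduction (days) | Share of 3-day target | False-positive rate |
|---|---|---|---|---|
| 3 years | 2% | 0.59 | 20% | 5.7% |
| 3 years | 5% | 1.43 | 48% | 9.0% |
| 3 years | 10% | 2.71 | 90% | 19.8% |
| 1 year | 2% | 0.20 | 7% | 5.1% |
| 1 year | 5% | 0.50 | 17% | 5.5% |
| 1 year | 10% | 1.00 | 33% | 6.9% |

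**Sensitivity to the unknowns.**

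- Gap of 2 years: 0.40, 0.98 or 1.90 days, with rates of 5.3%, 6.8% and 12.2%.
- Duration of intubation is compared only among intubated patients (section 2, Aim 2), so 22 versus 23 is a ceiling for that outcome. If about half are intubated (assumed 11 versus 12), the three-year rates at 5% and 10% yearly fall are about 7% and 12%. The spurious reduction in days does not change.

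**Effect on the future trial.** Suppose the pilot shows 3 days, of which 1.43 are drift (5% per year for three years). The true effect is 3 − 1.43 = 1.57 days, and 113 per group would then have about 31% power instead of 80%.

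**The case against.** Several objections stand and limit what can be said.

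- A reader might infer that three years of practice change has been built into the result. The documents do not show this. They give the end of enrolment but not its start, and no evidence that practice changed or in which direction. Only the conditional statement is supported: any change would be counted as e-stim effect.
- A reader might also infer that later control years are there for the asking. The database is described as existing and maintained, and extraction as automated, but the years it holds are not stated, and the quality group, not the study team, does the abstraction. The remedy has to be conditional on coverage.
- The 20% false-positive rate is the extreme of an assumed range. It needs a sustained 10% yearly fall, an SD that the protocol does not state, a 10-day mean taken from a cited outside study, and all 45 patients contributing. At a 2% yearly fall the rate is close to nominal.
- With several control years, it is tempting to fit a trend and subtract it. This is not sound here. With three annual means and SD 8, the slope SE is 8 / √23 / √2 = 1.18 days per year at an assumed 23 controls per year, and 8 / √100 / √2 = 0.57 at 100 per year. The assumed drift is only about 0.2 to 1.0 days per year.
- This is a pilot with feasibility as Aim 1 and openly historical controls. The 95% half-width is 2.017 × 2.39 = 4.8 days, larger than every drift shown.

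The last objection does not dispose of the point. Sampling error is visible in the confidence interval, whereas drift shifts the estimate without showing in it, and estimating an effect size for the randomised trial is a stated purpose.

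**Conclusion.** The point holds in conditional form. Restricting controls to 2016 while enrolling up to the end of 2019 confounds calendar time with treatment completely, over a gap of up to about three years, and the plan can neither detect nor correct a drift. Under the assumptions above, a yearly fall of 2% to 10% would produce a spurious reduction of 0.6 to 2.7 days against a 3-day target, with a false-positive rate of about 6% to 20% at full pilot size. Shortening the gap to one year reduces the spurious effect to 0.2 to 1.0 days and the rate to about 5% to 7%. These figures illustrate sensitivity; they do not estimate a bias that has occurred. The confounding itself follows from the stated dates and does not depend on them. The change is worth making because it directly serves the pilot's stated purpose.

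**What to change.** In section 6 (Historical Controls):

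1. Replace 2016 with the latest 12 months before the first e-stim enrolment as the main comparator, provided the quality database covers them. Otherwise use the most recent year held and state the reason.
2. Keep 2016 as a sensitivity comparison.
3. Ask the quality group to run the same query for each year from 2016 and return n, mean and SD for each outcome. These remain pooled, de-identified summaries, but the current restriction to means must be widened to allow n and SD.
4. Report the yearly figures descriptively as a check for drift, without subtracting a fitted trend.
5. State the enrolment start date, and state that recent controls reduce confounding by calendar time but do not remove it.

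The cost is a few more runs of the automated query, a revised paragraph and a slightly less simple control definition. No new patients, chart review or identifiable control data are needed.

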#### 7. Data

## a. Handling of Data

Data will be collected from the subjects' medical record in Epic, and from the mRS and GOSE instruments (completed by study staff). All data will be stored in REDCap. Data collected from the medical record will include demographics (sex, age, race), illness information (primary admission diagnosis, severity of critical illness as determined by the Sequential Organ Failure Score (SOFA) and/or APACHE II score), critical illness associated complications (e.g. deep vein thrombosis, hospital acquired infection, etc.), and medications associated with neuromuscular weakness (e.g. steroids, neuromuscular blockers, etc.). Data will be stored indefinitely.

## b. Sharing of Results with Subjects

No data will be shared with participants.

#### c. Data Banking

Repository Guardian: [name]. M.C.R.

Collection Information: At this time, no contributions to the Repository from outside investigators are planned. If this changes, a modification will be created with submittal requirements as needed.

Consent and Authorization: All subjects will have provided consent and authorization to participate in the research, including the storage and future analysis of their data (i.e., the consent and authorization documents will include appropriate repository language). The repository guardian or designee will ensure documentation of signed consents and authorizations, and maintain a tracking record for all data placed into this repository. Consent is required for participation in study and repository together. No biospecimen or genetic material will be collected—only clinical data. The historical data will not be included in the repository. This repository will collect data from this study only, for the purpose of using in future analyses pertaining to e-stim treatment and intubation. The repository will collect identifiable information, but identifiable information will not be released to other investigators.

Maintenance Information: All data will be assigned a unique, subject code as described in the Privacy, Confidentiality and Data Security section in this protocol. The key to the code will be limited only to the

repository guardian or designee, and it will be stored separately from signed consent forms. Any email correspondence will be encrypted.

Electronic security: Associated data will be held securely in compliance with OHSU's Information and Security Guide. Specifically, data will be held on OHSU networked drives, behind the OHSU firewall. Files will be password-protected. We plan to utilize REDCap as the database.

If a subject withdraws consent, the repository guardian or designee will destroy (delete) their data to ensure no future use.

Repository guardian: The repository guardian is [name]. She will be responsible for ensuring that data are received and released according to OHSU policy and the IRB approved repository protocol. The repository guardian is responsible for:

- Ensuring that the data are received and released according to OHSU policy and the IRB approved protocol.
- Executing a repository sharing agreement each time data are released for research purposes.
- Ensuring the security and confidentiality of stored data.
- Ensuring the security and confidentiality of data during transfer.
- Tracking acquisitions and releases of data.
- Maintaining methods for identifying data for which consent has been withdrawn and ensuring no future use
- Identifying data that have limitations on future uses and ensuring that future uses are not contrary to those limits.

Release Information: Requests for data will first be discussed with the repository guardian or designee to ensure that the nature, quality, and number of data available will meet the scientific needs of their research. Prior to any release, the repository guardian or designee will verify that there were no restrictions placed on the use of the data by the IRB, or by the participant. The repository guardian or designee will verify current IRB approval for each recipient research protocols, and ensure a Repository Sharing Agreement is executed each time data are released for research purposes. All data released from this repository will be tracked, including date of release, IRB approved documents, description of data, and Repository Sharing Agreement signed. Only deidentified data will be released to other investigators. If materials are transferred outside of OHSU, the repository guardian or designee will verify that a materials transfer agreement is in place prior to release. Any email correspondence will be encrypted.

# 8. Data Analysis Analysis plan

Covariates The following factors may impact outcome, and thus will be collected to assure the groups are comparable:

i. Demographics (sex, age, race)

Version Date 7/22/19

- ii. Illness information: primary admission diagnosis, severity of critical illness (Sequential Organ Failure Score (SOFA), APACHE II score)
- iii. Critical Illness Associated Complications Complications such as deep vein thrombosis, Hospital Acquired Infection, etc. will be recorded as these conditions may impact outcome.
- iv. Medications associated with Neuromuscular weakness: including but not limited to steroids, neuromuscular blockers

#### **Group Comparisons**

The study team statistician will analyze the data, and will be blinded to treatment assignment ("Group A" and "Group B", instead of "E-Stim Group" "Historical Controls"). Descriptive statistics will be used to quantify feasibility. Mean length of stay and mean duration of intubation will be compared between the e-stim group and the historical controls using a t-test. If necessary, a linear regression model for length of stay and/or intubation duration will be used to compare between groups while controlling for the potential confounding of covariates. A Wilcoxon rank-sum test will be used to compare the exploratory functional outcome measures between groups, as the mRS and GOSE are both ordinal scales.

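### The Group A and Group B labels cannot blind the statistician, and the covariate adjustment has no fixed rule, so the analysis should not be reported as blinded and the Aim 2 model should be fixed in advance

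*Combined protocol and SAP*

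**What the plan says.** Section 8, Group Comparisons, says that the study team's statistician "will be blinded to treatment assignment". The only masking step described is the neutral group label. The same paragraph plans a t-test on mean length of stay and mean intubation time without condition, and then adds: "If necessary, a linear regression model for length of stay and/or intubation duration will be used to compare between groups". It gives no criterion for necessity, no model and no time for the decision.

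Section 8, Covariates, lists sex, age, race, primary diagnosis, SOFA and APACHE II. It then adds two open-ended categories: complications of critical illness, and drugs linked to neuromuscular weakness.

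Section 6, Historical Controls, plans to "identify patients cared for in the Neuro ICU during the year 2016". On the source it says "The ICU quality group will abstract data for us", by automated extraction without chart review. The research team is to receive "only means from the historical controls on data such as length of stay and hospital costs", a limit that section 4 repeats.

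For enrolled subjects, section 7a describes individual data from Epic and from mRS and GOSE forms that study staff complete: "All data will be stored in REDCap". Section 5a dates the prospective cohort: "We will end enrollment at the end of the 2019 calendar year".

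**The concern.** In a non-randomised comparison with historical patients, whether to adjust, and for what, can largely determine the estimate. A blinded analyst would give some protection against choosing the model that favours the intervention. Here the blind exists in name only, and the choice it might have protected is left open.

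Two things are at stake. A report that calls the analysis blinded would claim a safeguard that the design cannot supply. And the pilot exists to give an effect size for a full trial (sections 2 and 4), so an estimate selected after seeing the results would carry into that trial's sample size.

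**Working it through.** **1. Can the labels hide the groups?** Setting the sections side by side:

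- *Form of data.* Controls: means only (sections 4 and 6). E-stim: one record per subject (section 7a). A table of means cannot be mistaken for patient records.
- *Calendar period.* Controls: 2016. E-stim: prospective, closing at the end of 2019. The start date is not given, but any record dated after 2016 belongs to the e-stim group.
- *Treatment delivery.* Aim 1 measures the share of planned sessions delivered, against an 80% threshold (section 2). Such data exist for e-stim subjects only.
- *Functional scales.* The study team scores mRS and GOSE at Neuro ICU discharge in enrolled subjects (section 6). No source is described for controls.
- *Group size.* 22 and 23 are printed with their identities (section 8, Power Calculation). This is a weak clue alone, but section 5a lets e-stim enrolment stop short of 22.

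No removal of dates, common data layout or separate feasibility analyst is described. If patient-level control rows replaced the means, the first clue would go and the others would remain.

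**2. What is left open?** The trigger, the covariate set and the timing. Some listed covariates (complications, medications) may arise after stimulation starts. Adjusting for them could remove part of a treatment effect, so the open choice covers the kind of covariate as well as the number.

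**3. Can the choice be made on the planned data?** Not on means alone. Patient-level regression needs individual outcomes and covariates for both groups. The model-choice risk is therefore conditional on patient-level control data being supplied.

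**4. The plan's figures.** Pilot size: 0.20 × 226 = 45.2, and 22 + 23 = 45, so it reproduces. The 113 per group cannot be checked, because no SD is given. With a two-sided 5% level (sidedness is not stated), 80% power and a 3-day difference, the implied common SD is 3 × √(113/2) / (1.960 + 0.842) ≈ 8.05 days.

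**5. Precision.** SE of a difference = SD × √(1/22 + 1/23) = SD × 0.298. For assumed SDs:

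| SD (days) | SE (days) |
|---|---|
| 7 | 2.1 |
| 8 | 2.4 |
| 9 | 2.7 |

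This describes sampling error of one estimate. Intubation time applies only to subjects who were intubated, so its SE would be larger at the same SD if some were not.

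**6. Illustration of free choice, if patient-level rows exist.** 20,000 simulated trials per setting, 22 v 23, normal outcome, no group effect, no confounding, 3 or 6 covariates explaining 10%, 30% or 50% of variance:

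- unadjusted Welch test alone, or adjusted regression alone: type I error about 4.5% to 5.3%;
- the smaller p-value of the two: 6.6% to 8.5%.

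These are simulation results under stated assumptions, not figures from the plan. They cover a choice between two analyses only; four optional covariates would already allow 2⁴ = 16 models per outcome.

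**The case against.** The strongest reply is that the harm cannot arise on the data described. The statistician belongs to the study team, the team receives only control means, and no regression can be fitted to them. This stands, and it limits the model-choice part of the point. It does not rescue the blind, because means make the control group more obvious. It also exposes a separate and larger inconsistency between sections 4 and 6 and the regression in section 8.

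Second, the plan is less open than it may look. The unadjusted t-test is unconditional, six covariates are named, and the stated purpose of checking that the groups are comparable hints at imbalance as the trigger. That is fair, but no threshold or rule follows from it.

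Third, this is a pilot that estimates an effect, not a confirmatory test. That lowers the severity. It does not make a blinding claim accurate.

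A reader might infer three stronger statements that the documents do not support:

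- *That adjustment will be decided with the groups known.* The documents do not say when it is decided, and a rule written before data receipt would prevent this.
- *That the same statistician must analyse feasibility.* The sentence on feasibility names nobody. Section 9 has biostatistical consultants doing double entry, but does not say whether the statistician is among them.
- *That the SE shows estimates moving by a day or more between models, against a 3-day target.* The SE does not measure movement between models, and the 3 days is the future trial's ventilation effect, not a pilot criterion.

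**Conclusion.** The point holds in two parts of different strength. First, without condition: labels alone cannot conceal which group is which, so the analysis should not be described as blinded. This rests only on the plan's own account of its data sources. Second, conditionally: if patient-level control data are obtained, the decision to adjust may be made with groups and outcomes visible, because no rule fixes it beforehand. The documents give no figure for the resulting bias. The 6.6% to 8.5% error rate is an illustration that depends on the simulation assumptions, and the SE of 2.1 to 2.7 days (SD 7 to 9, assumed) describes precision only. The change should be made, but it is secondary to settling what control data will be supplied.

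**What to change.** 1. In Group Comparisons, delete the blinding statement and call the analysis open-label with a fixed plan. Alternatively, describe masking that could work: a common data layout, dates removed, and a separate analyst for feasibility.
2. Replace the conditional regression with a rule. The Aim 2 estimate is adjusted for a short named list of pre-treatment covariates already planned for collection, for example age, APACHE II and primary diagnosis category, with the planned unadjusted difference shown beside it. Section 7a allows SOFA or APACHE II, so whichever is chosen must be recorded for everyone. Keep complications and medications that arise after treatment starts out of this model.
3. Date the model before control outcomes are released, or state that they were already available.
4. Reconcile sections 4 and 6 with section 8 so that the quality group supplies de-identified patient-level control rows holding the named covariates. Without them the adjustment cannot be run.

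Cost: new wording, a dated sign-off and a revised data request to the quality group, which may need ethics board agreement. The documents do not say whether the 2016 database holds every covariate, so this must be confirmed before the list is fixed. The team gives up later freedom over the model and, unless real masking is set up, the word blinded in its report. No extra subjects or study procedures are needed.

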## **Power Calculation**

We plan a future trial to determine the efficacy of electrical stimulation to reduce days of mechanical ventilation by 30% (from 10 days to 7 days, observed in the Routsi study). Estimated sample sizes for a two-sample means test (Satterthwaite's t test) assuming unequal variances, with an 80% power to detect a 30% difference in days of mechanical ventilation with a significance level of p=0.05, would require 113 patients in each group (for a total of 226 subjects). In order to prepare for this future RCT, we propose a pilot trial of 45 subjects (20% of the full sample size), with 22 patients in the intervention group (e-stim) and 23 historical controls.

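### The team is to receive only means for the historical controls, yet the analysis plan specifies tests that need SDs or patient-level control data; the expected precision of the pilot is also not stated

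*Combined protocol and SAP*

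**What the plan says.** Two sections describe the control data. Section 4 (Study Design) and the Historical Controls part of section 6 both say that the research team will not see identifiable control data, but "only means from the historical controls on data such as length of stay and hospital costs". Historical Controls adds that an automated query will be used "to capture average length of stay and length of ventilator support for the purposes of comparison", and that individual charts will not be reviewed. It does not list mRS, GOSE or the section 8 covariates among the control data.

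Section 8, Group Comparisons, sets out the analysis by the study team's statistician:

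- For Aim 2: "Mean length of stay and mean duration of intubation will be compared between the e-stim group and the historical controls using a t-test".
- As a conditional further step, where judged to be needed, "a linear regression model for length of stay and/or intubation duration will be used to compare between groups", with adjustment for covariates.
- For Aim 3: "A Wilcoxon rank-sum test will be used to compare the exploratory functional outcome measures between groups".

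Section 4 gives the purpose of the pilot as "to estimate the effect size to power a future, full scale randomized controlled trial of electrical stimulation". The Power Calculation takes 113 per group (226 in all) for the future trial, to detect a fall from 10 to 7 ventilator days with 80% power at 0.05. It then proposes "a pilot trial of 45 subjects (20% of the full sample size), with 22 patients in the intervention group (e-stim) and 23 historical controls". It gives no SD, and no confidence interval or target half-width for the pilot.

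**The concern.** A mean carries no information about spread. If the team receives only control means, it can form a difference between groups but cannot attach a standard error to it, cannot adjust it and cannot rank individual outcomes. Aims 2 and 3 could then not be analysed as section 8 describes. The likely improvisation would be to test the e-stim patients against the control mean as if that were a known constant, which leaves out the controls' sampling error.

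The stated purpose is to estimate an effect size, and an estimate is of use to trial planners only with its uncertainty. The plan justifies 45 subjects only as a fraction of 226, so a reader cannot tell how well the effect will be known at the end.

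**Working it through.** **1. What each planned analysis needs, against what is released.**

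| Analysis (Group Comparisons) | Needed from controls | Described as released |
|---|---|---|
| Two-sample t-test or CI, length of stay and intubation duration | n, mean, SD | mean |
| Linear regression with covariates | patient-level outcome and covariates | mean; covariates not listed |
| Rank-sum test, mRS and GOSE | patient-level scores or counts per category | neither scale listed |

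The missing SD decides the result. Take means 7 and 10, n = 22 and 23, and an assumed e-stim SD of 8. Then t = 3/√(8²/22 + SD_c²/23), and the Welch p-value is 0.11 for a control SD of 3, 0.22 for 8 and 0.51 for 20.

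**2. The plan's own sample size.** The 113 per group cannot be reproduced forward because no SD is given. Solved backward (difference 3 days, 80% power, 0.05 assumed two-sided, equal SDs, t distribution), it implies a common SD of 8.01 days. Check by the normal formula: n = 2 × 7.849 × 8.01²/3² = 112, and the t correction brings this to 113. A one-sided test would imply 9.04. The pilot size does reproduce: 0.20 × 226 = 45.2, and 45/226 = 19.9%.

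**3. Expected precision if n and SD were available.** Half-width = t × SD × √(1/n₁ + 1/n₂), with SD 8.01. Intubation duration is taken to be the same quantity as ventilator days.

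- 22 v 23, all intubated: SE = 8.01 × √(1/22 + 1/23) = 2.39; × 2.017 = 4.8 days.
- 11 v 12, an assumed half intubated: SE = 8.01 × √(1/11 + 1/12) = 3.35; × 2.080 = 7.0 days.

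The second case matters because Aim 2 limits this comparison to intubated subjects, while the inclusion criteria do not require intubation. The documents give no intubation rate. At an SD of 6 the first figure is 3.6 days; at 10 it is 6.0.

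**4. If the control mean were treated as fixed.** The half-width would be 2.080 × 8.01/√22 = 3.6 days instead of 4.8. Under no true difference, the one-sample statistic is distributed as √(1 + 22/m) times a t variable with 21 df, where m is the number of controls behind the mean (normal data, equal SDs).

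- m = 23: √(1 + 22/23) = 1.399. Rejection occurs when |t| > 2.080/1.399 = 1.487, so the false-positive rate is 15%.
- m = 200 (assumed): √(1 + 22/200) = 1.054. The cut-off is 1.974 and the rate is 6%.

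Skewed (gamma) data give about 16% with 23 controls and 8 to 10% with 200, depending on the assumed mean. Unequal SDs with about the same total variance move the 15% to 24% (6.5 e-stim, 9.3 control) or 10% (reversed).

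**The case against.** The strongest reply is that the means-only sentence is a privacy statement: it contrasts means with identifiable data. Elsewhere the plan speaks of pooled, de-identified historical patients, collects covariates to check that the groups are comparable, and has the statistician work blinded on Group A and Group B. All of that fits patient-level, de-identified data. This stands as a reason not to conclude that the tests can never be run. It does not remove the problem: no section grants SDs or patient-level values, two sections say means only, and the statistician belongs to the study team.

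Four stronger readings are tempting, and the documents do not support them.

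- A reader might infer that the trial will run a test at three times its nominal error rate. The plan contains no one-sample test, and the 15% holds only if the control mean comes from 23 patients.
- A reader might infer that the future trial will be sized on the pilot's point estimate. Estimating an effect size is the stated purpose, but the Power Calculation uses an external 30% target, and no section says the pilot result will replace it.
- A reader might infer that 113 per group is wrong. It cannot be checked without the SDs, which is not the same thing.
- A reader might count low power as an error. In a pilot it is not, and 20% is a correct headcount.

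It is also fair to say that every half-width here rests on a back-solved SD and concerns ventilation only, not length of stay.

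**Conclusion.** The concern holds as a contradiction between sections. The control data described in Study Design and Historical Controls do not support any of the three analyses in Group Comparisons, and the passages must be reconciled. This conclusion rests on the text alone and needs no assumed figure. It should be corrected before analysis. The feasibility aim is unaffected.

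The secondary point also holds: no expected precision is given for an effect size that the pilot exists to estimate. At the implied SD of about 8 days (two-sided, equal SDs), the half-width is about 4.8 days in the best case and about 7.0 days if half are intubated. Both exceed the 3-day target. Treating the control mean as fixed would not be a safe way out: the false-positive rate would be about 15% with 23 controls and about 6 to 10% with an assumed 200.

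**What to change.** 1. **Study Design and Historical Controls.** State that the quality group will release at least n, mean and SD for length of stay, and for intubation duration among intubated patients. Preferably it would release de-identified patient-level values with the section 8 covariates and, if the database holds them, mRS and GOSE (or counts per category). Where an item cannot be released, amend Group Comparisons to drop the corresponding test and describe that outcome only.
2. **Group Comparisons.** Where n and SD are available, report each Aim 2 difference with a 95% CI.
3. **Power Calculation.** Give the expected half-width on ventilation for 22 v 23 and for a stated assumed intubated fraction, with the SD used. Label the 20% as a headcount. Say that the size of the future trial will take account of this uncertainty.

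The cost is a larger data export, which needs the quality group's agreement and any approval that requires. Patient-level covariates and functional scores are the demanding part, since no chart review is planned; n and SD are the minimum. The stated precision will look less favourable. No extra patients are enrolled.
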